The same slice thickness and contrast material type & dose should be maintained throughout the entire study. The NovoTTF-200A System and all components including the transducer arrays must be removed and cannot be brought into the MR environment.

- 10. Device compliance (if applicable)

Once every 8 weeks, for one year or until intracranial failure (whichever comes first) the following

neurocognitive tests will be performed:

1. HVLt-R
2. TMT Part A and B

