1. EORTC QLQ C30
2. EORTC BN20 addendum

c) Follow up 8 weeks from treatment termination

1. KPS score recording
2. Physical examination and vital signs
3. Neurological examination
4. Complete blood count including differential
5. Serum chemistry panel, including:
 1. BUN, Creatinine
 2. Sodium, Potassium
 3. ALT, AST, Bilirubin
6. Adverse event collection and recording
7. Concomitant medication recording
8. A high resolution, isovolumetric T1-weighted post-gadolinium MRI of the brain using a 3T MR scanner. Additional parameters include:
 - a) FOV: 256 mm x 256 mm
 - b) Matrix: 256x256
 - c) Slice thickness: 1 mm
 - d) Full brain coverage

The same slice thickness and contrast material type & dose should be maintained throughout the entire study. The NovoTTF-200A System and all components including the transducer arrays must be removed and cannot be brought into the MR environment.

Please see **Section 9.a** and **Appendix B** for details about the neurocognitive function assessments.

Following Study Treatment Discontinuation

Patients will have additional follow-up outside of scheduled study follow-up at the discretion of the treating physician.

Post Intracranial Failure Follow-up

Following intracranial failure, patients will be followed every 4 weeks for survival (this can include telephone call follow-up and does not require a clinical visit). Patient death date will be captured in the CRFs.

Foreseeable Factors That May Compromise the Outcome of the Clinical Investigation or the Interpretation of Results

There are no foreseeable factors that may compromise the outcome of the clinical investigation or the interpretation of the study results.

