- Time to neurocognitive failure, as measured by cognitive decline on a battery of tests: HVLT-R free recall, delayed recall, and delayed recognition; COWAT; and TMT Parts A and B.
- Neurocognitive failure-free survival, defined from the date of starting NovoTTF-200A to neurocognitive failure (as measured by HVLT-R free recall, delayed recall, and delayed recognition; COWAT; and TMT Parts A and B) or death (whichever occurs first), censored at the last neurocognitive assessment on which the patient was reported alive without neurocognitive failure.
- Quality of Life using the EORTC QLQ C30 with BN20 addendum.
- Toxicity during NovoTTF-200A treatment based on incidence and severity of treatment emergent adverse events as evaluated using the CTCAE version 5.0 (**Appendix D**).

The above battery of neurocognitive instruments has been selected based on accepted standardization and psychometric principles, published normative data relative to routine demographics, relevance to general neurocognitive status, minimal practice effects, and brevity of the overall battery. Additionally, similar variations of this neurocognitive testing battery have been utilized in multiple cooperative group trials including RTOG 0212, RTOG 0214, RTOG 0424, RTOG 0525, RTOG 0933, ACOSOG Z0933,

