NCCTG N0574, NCCTG N0577, RTOG 0825, ECOG E3F05, NCCTG N0874/ABTC 09-0, and N107C. Assessments will be conducted every 8 weeks for the first year or until intracranial failure, whichever occurs first. The HVLt-R test has been used and validated in multiple prior phase III trials of patients with brain metastases [9, 21]. HVLt-R incorporates 6 different forms, helping to mitigate practice effects of repeated administrations. Each form includes 12 nouns (targets) with 4 words drawn from 3 semantic categories, which differ across the 6 forms. The test involves memorizing a list of 12 targets for 3 consecutive trials (immediate recall), recalling the 12 targets after a 20-minute delay (delayed recall), and identifying the 12 targets from a list of semantically related or unrelated items (delayed recognition). In COWAT [Johnson SC et al, *Clin Neuropsychol.* 2012; 26(7):1230-41, Johnson DR et al, *Neuro Oncol.* 2012;14(6):808-16], the patient produces as many words as possible in 1 minute for a specific letter and the test assesses language and executive/frontal skills. The test is widely used and is part of the Halstead-Reitan Neuropsychological Battery. Impairment in the understanding of language or the motor expression of language will impair the results in this trial. Since such functions are affected by brain-directed therapies such as WBRT, the test could be sensitive to the experimental treatment effects on those functions. TMT [Bowie CR and Harvery PD, *Nat Protoc.* 2006; 1(5):2277-81] is a measure of visuospatial scanning, attention, sequencing and cognitive processing speed (Part A) and executive function (Part B). Those neurocognitive functions could be affected both by brain metastasis and by therapies directed to the brain, and will therefore be used in the trial. Patients must “connect the dots” either in a numbered sequence or alternating letters and numbers.

b) Sample Size Determination: Because the primary endpoint is feasibility, the proposed sample size is not driven by statistical hypotheses. Rather, we propose the sample size of 25 so that we will have precise enough information for planning the next phase of treatment development. The following table summarizes the point estimate and 95% confidence interval when n=25.

# patients continuing therapy	10	15	18	20
Point estimate	40%	60%	72%	80%
95% confidence interval	23% - 59%	41% - 77%	52% - 86%	61% - 91%

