Appendix B: Neurocognitive Function

According to Meyers and Brown (Meyers CA 2006), for a neurocognitive test battery to be useful in clinical research it should fulfill the following 6 criteria:

- a) It should be brief in order to reduce patient and clinical burden.
- b) It should have alternate forms of the tests in order to reduce practice effects and therefore allow for repeated test administration.
- c) It should have good psychometric properties such as validity, reliability, and population norms so that true changes in NCF above fluctuations due to situational factors can be detected.
- d) It should be sensitive to changes in cognitive function.
- e) It should be highly standardized and easy to administer so that no specialized psychological training is necessary in order to be able to administer the test battery.
- f) Most patients should be able to complete the neurocognitive tests, even patients with significant neurocognitive problems, in order to reduce the likelihood of selection bias.

See Statistical Considerations chapter for further information regarding the evaluation of neurocognitive endpoints

Test Battery for Neurocognitive Function

Neurocognitive Parameter Measured	Test	Time to Administer (Minutes)
Auditory/verbal learning and memory	Hopkins Verbal Learning Test-Revised	5
Visual-Motor Scanning Speed	Trail Making Test Part A	5
Executive Function	Trail Making Test Part B	5
Verbal Fluency	Controlled Oral Word Association Test	5
	Total Time	20

Prior to initiation of TTFs, all patients will undergo baseline neurocognitive testing using these neurocognitive instruments. At that time, history regarding level of education reached will also be obtained. After completion of therapy, all patients will undergo this neurocognitive test battery, conducted by trained and certified nurses or clinical research associates, every 8 weeks until death or until one year after therapy, whichever comes first. In the analysis of neurocognitive decline, each patient will serve as his/her own control, as decline for each neurocognitive test at each follow-up time point will be compared to baseline.

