Appendix C: Study Calendar

	T=(-21)-0 Days (Baseline)	T=0 days (Registration to Treatment)	T= 0 to 21 days (Registration to Treatment to 21)	T=every 8 weeks until intracranial failure (Follow-Up) (±7days)	T= 8 weeks from treatment termination (±7days)	T= every 4 weeks from treatment discontinuation (±7 days)
Signed ICF	X					
MRI of brain ¹	X			X	X	
Medical history	X					
Performance Status (KPS score)	X			X	X	
Physical examination ²	X			X	X	
Neurological examination	X			X	X	
Complete blood count including differential	X			X	X	
Serum chemistry panel ³	X			X	X	
Neurocognitive Testing ⁴	X			X		
Quality of Life Questionnaire ⁴	X			X		
Serum pregnancy test ⁵	X					
Blood coagulation test ⁶	X					
Registration to treatment (Start of use of NovoTTF-200A)		X				
Adverse event collection and recording ⁷		X	X	X	X	
Concomitant medication recording	X	X	X	X	X	
Device compliance assessment				X		
Telephone follow-up for survival						X

1. A high resolution, isovolumetric T1-weighted post-gadolinium MRI of the brain using a 3T MR scanner. **Treatment with the NovoTTF-200A System is to begin within 21 days after this baseline MRI.** Additional parameters include:

- FOV: 256 mm x 256 mm
- Matrix: 256x256
- Slice thickness: 1 mm
- Full brain coverage

The same slice thickness should be maintained throughout the study. The NovoTTF-200A System and all components including the transducer arrays must be removed and cannot be brought into the MR environment.

2. Vital signs are included as part of the physical exam
3. Serum chemistry panel includes: BUN, Creatinine, Sodium, Potassium, ALT, AST, Bilirubin
4. Neurocognitive Testing and QOL questionnaire will be performed for one year or until second cerebral progression (whichever comes first)
5. If applicable and within 14 days
6. Coagulation tests include PT, PTT and will be performed as part of the follow up procedures only if clinically indicated
7. Reporting period will begin immediately following registration to treatment (start of use of NovoTTF-200A) and ends at the conclusion of 8 weeks following treatment termination

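### Neurocognitive failure-free survival counts deaths without time limit after cognitive testing has stopped, so patients who die are credited with untested months and the curve beyond week 48 is an artefact

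*Combined protocol and SAP*

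**What the plan says.** Section 9(a), repeated in Section 6 under Outcome Measures, starts the clock at first use of the device. The event is neurocognitive failure or death, whichever is first; a patient without an event is "censored at the last neurocognitive assessment on which the patient was reported alive without neurocognitive failure". No limit is set on the time between the last test and a death.

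The documents give the testing window in four places:

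- Section 9(a): "Assessments will be conducted every 8 weeks for the first year or until intracranial failure, whichever occurs first".
- Section 7(b): "Once every 8 weeks, for one year or until intracranial failure (whichever comes first) the following" tests are done. The Appendix C grid agrees: after baseline, cognitive tests appear only in the column that runs until intracranial failure, and not at the visit 8 weeks after treatment termination.
- Appendix B, after completion of therapy: "every 8 weeks until death or until one year after therapy, whichever comes first".
- Appendix C footnote 4: "Neurocognitive Testing and QOL questionnaire will be performed for one year or until second cerebral progression (whichever comes first").

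Deaths are still collected after testing stops: "Following intracranial failure, patients will be followed every 4 weeks for survival", by telephone if need be. Section 6 allows whole-brain radiotherapy in that period, and Section 9(a) says of the functions tested by the Trail Making Test: "Those neurocognitive functions could be affected both by brain metastasis and by therapies directed to the brain".

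Section 9(d) adds no rule for stopped tests. It says only that the remaining time-to-event endpoints are handled like those it has described (cumulative incidence and Kaplan-Meier).

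**The concern.** The two halves of the endpoint are observed over different periods. Death is followed to the end of the study. Cognition, under Sections 7(b) and 9(a), is followed only until intracranial failure or one year. The interval that is not tested is one in which the plan itself expects cognition may change.

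Three things follow. Untested time counts as failure-free for patients who later die. Patients with the same tests are scored differently according to whether they die before data cut, so censoring depends on the outcome. And once testing has ended for everyone, the at-risk group is selected on the event. Time to neurocognitive failure has a related gap: patients with intracranial failure leave observation, and the plan names only death as a competing risk.

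At stake is the reading of a curve that joins intracranial control and cognition, the two features on which Section 3(e) bases its interest in the device.

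**Working it through.** **The plan's own figure.** None is given for this endpoint. The only precision figures are the 95% intervals for the feasibility proportion at n = 25. The Wilson interval is (p + z²/2n ± z√[p(1−p)/n + z²/4n²]) / (1 + z²/n). For 15 of 25, with z = 1.96, the centre is (0.600 + 0.077)/1.154 = 0.587 and the half-width is 1.96 × √(0.0096 + 0.0015)/1.154 = 0.179. That gives 40.7% to 76.6%, against 41% to 77% in the table. The other three columns also reproduce. The half-width of about 18 points is a yardstick below.

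**Last scheduled test.** Eight-weekly visits within 52 weeks number 52/8 = 6.5, so six; the last is at week 48.

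**Two patients alike up to week 16.** Both have clean tests, and intracranial failure is found at week 16 (16 × 7/30.44 = 3.7 months). I assume the battery is given at that visit, since MRI and tests share a calendar column; the text does not settle this.

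| Later course | Scored as | Untested months credited |
|---|---|---|
| Dies at month 12 | Event at 12.0 | 12.0 − 3.7 = 8.3 |
| Alive at data cut | Censored at 3.7 | 0 |

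**The tail.** Event-free survivors are all censored at or before week 48, and no test can record a failure after it. Suppose k patients have times beyond week 48. All are deaths. After the i-th death the Kaplan-Meier value is S(48) × [(k−1)/k] × [(k−2)/(k−1)] × … = S(48) × (k−i)/k, which is zero at i = k. With k = 5, for example, the curve falls by one fifth of S(48) at each death and ends at zero, however many patients are alive and well. No assumption about cognition is needed. If k = 0 the curve simply ends.

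**Size before the tail.** This needs simulation. From the documents: 12-month brain-metastasis risk and median survival in the two prophylactic-irradiation trials (Section 3(a)), and 12 to 36 months of follow-up (24-month accrual, 36-month study). Assumed, because the documents give neither: median survival after intracranial failure, and median time to cognitive failure before/after it. Times are exponential, with 200,000 patients per scenario. The comparator is the same 8-weekly testing continued past intracranial failure to one year, so ordinary detection lag is not counted as bias.

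| Brain mets at 12 mo; median survival (mo) | Assumed survival after failure (mo) | Assumed cognitive medians before/after (mo) | 6 mo: as written vs continued | 12 mo: as written vs continued |
|---|---|---|---|---|
| 58.0%; 15.1 | 6 | 12/3 | 59.3 vs 54.5 (+4.8) | 30.1 vs 23.6 (+6.5) |
| 58.0%; 15.1 | 9 | 12/3 | 56.6 vs 51.1 (+5.5) | 29.1 vs 20.7 (+8.4) |
| 32.4%; 10.1 | 4 | 12/3 | 49.3 vs 47.1 (+2.2) | 21.3 vs 18.9 (+2.4) |
| 40.4%; 5.4 | 2.5 | 12/3 | 32.8 vs 30.6 (+2.2) | 8.9 vs 7.5 (+1.4) |
| 58.0%; 15.1 | 6 | 12/12 | 61.9 vs 60.6 (+1.3) | 32.4 vs 30.4 (+2.0) |
| 58.0%; 15.1 | 6 | 24/6 | 70.0 vs 66.9 (+3.1) | 41.2 vs 36.0 (+5.2) |
| 32.4%; 10.1 | 6 | 24/6 | 57.1 vs 55.3 (+1.8) | 29.3 vs 26.5 (+2.8) |

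Across these runs, 23% to 46% of patients (25 × 0.23 = 5.8 to 25 × 0.46 = 11.5 of 25) have as their event a death after intracranial failure with no observed cognitive failure. They carry a mean of 3.1 to 7.1 untested months. Further runs with other assumed inputs gave about 0 to 5 points at 6 months and −2 to +6 at 12 months. Negative values arise when intracranial failure barely changes the cognitive hazard: pulling survivors back to their last test then outweighs the credit to those who die.

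**Alternative scorings in the same seven runs.** Counting intracranial failure as an event falls below the comparator at 6 months by 5.4 points (47.1 − 41.7) to 17.1 points (60.6 − 43.5). Censoring at the last test any death more than 16 weeks after it lies between −1.1 (59.5 − 60.6) and +2.7 (53.8 − 51.1) at 6 months, and below the comparator by 0.6 (20.7 − 20.1) to 6.3 (30.4 − 24.1) at 12 months. Neither is neutral.

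**The case against.** The premise is not settled. Appendix B would test beyond intracranial failure, until death or a year after therapy, and much of the untested time would disappear. Footnote 4 would also test past a first intracranial failure, although its one-year stop leaves the tail after week 48. This objection stands: the point holds under Sections 7(b) and 9(a), and the first defect is that four statements of one window disagree.

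The effect is also small for the data. Even the largest excess in the table is less than half the 18-point half-width of an interval at n = 25. This is one of nine secondary endpoints, it is descriptive, and no 6- or 12-month estimate of it is planned. That stands too, and it limits the importance.

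A reader might infer more: that the endpoint systematically flatters the device in patients whose prophylaxis failed, and that the inflated figures would be set against cranial irradiation. The documents do not support this. They give no time to cognitive failure, no change in its hazard after metastasis and no survival after intracranial failure, so even the sign at 12 months is not guaranteed. Section 3(e) makes the next study depend on safety and tolerability, not on this curve.

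A reader might also conclude that intracranial failure should become an event in the main definition. That would be fully observed, but it is a different and lower estimand and overlaps intracranial failure-free survival, which is already planned.

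**Conclusion.** The concern holds in limited form. Under the testing stop in Sections 7(b) and 9(a), the scoring credits untested months to patients who die and not to those who survive, and the curve beyond week 48 is an artefact. Both follow from the wording alone, the second provided at least one death is recorded after week 48.

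The numerical effect is assumption-driven: roughly 0 to 5 points upward at 6 months and about −2 to +8 points at 12 months (5.5 and 8.4 in the most extreme scenario). It depends chiefly on how far intracranial failure raises the cognitive hazard and on how long patients live afterwards. The primary endpoint and sample size are unaffected. The change is worth making because a stated rule yields a wrong curve and can be corrected in text.

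**What to change.** Amend Section 9(a) and the matching text in Section 6:

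1. Reconcile the testing window across Sections 7(b) and 9(a), Appendix B, and the Appendix C grid and footnote 4.
2. Truncate neurocognitive failure-free survival at the last scheduled test (week 48 under 9(a)) and report no curve beyond it. State how a patient who dies after that point enters the earlier part of the curve, so that this patient and a survivor with the same tests are scored alike.
3. For time to neurocognitive failure, where testing stops at intracranial failure, treat intracranial failure as a competing event alongside death in the cumulative incidence function.
4. Report two sensitivity analyses, not as the main definition: one in which intracranial failure is also an event, and one that censors at the last test any death more than 16 weeks after it. Truncation does not remove the credit before week 48; these analyses show how much the result depends on it.

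Neither Section 9(a) nor Appendix B states what size of decline is a neurocognitive failure. That threshold is needed before any of these rules can be applied.

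Cost: items 2 to 4 are wording and use dates already collected. Item 1 adds tests only if the reconciled window runs past intracranial failure. The price is that there is no estimate beyond week 48, hence none at 12 months, and that time to neurocognitive failure then describes failure before intracranial failure only.

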c) Statistical Analysis – Primary Endpoint: Since this is a feasibility study, we will not attempt a strict control of multiplicity in analyses of the primary and secondary endpoints. Proportion of patients continuing TTF will be estimated using Wilson’s method and a one-sided 95% confidence interval will be reported. We will also summarize this measure for those who had PR and CR separately.

d) Statistical Analysis – Secondary Endpoints

Secondary endpoints for statistical testing: Time to intracranial failure with death as a competing risk will be estimated using cumulative incidence function (CIF) and reported with a one-sided 95% confidence interval. Rate of intracranial failure at a given time will be estimated using the CIF. Overall survival will be estimated using the Kaplan-Meier method. Other time-to-events data (with or without competing risks) will be analyzed similarly. Quality of life will be treated as a continuous endpoint; its mean will be estimated and reported with a 95% confidence interval. Toxicity (CTCAE 0-4) will be tabulated.

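### A patient too impaired to attempt the cognitive battery is not recorded as a neurocognitive failure, so the neurocognitive secondary endpoints understate decline by an unknown amount

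*Combined protocol and SAP*

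**What the plan says.** Three secondary endpoints depend on the cognitive battery: the rate of decline at 2, 4, 6, 8, 10 and 12 months, time to neurocognitive failure, and neurocognitive failure-free survival.

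- **Definition of failure.** Section 9(a) has "Time to neurocognitive failure, as measured by cognitive decline on a battery of tests", and Section 6 (Outcome Measures) says the same. Appendix B adds that "decline for each neurocognitive test at each follow-up time point will be compared to baseline". No threshold, number of tests or non-test criterion is given.
- **Censoring.** Failure-free survival runs to the earlier of test-based failure and death; otherwise the patient is "censored at the last neurocognitive assessment on which the patient was reported alive without neurocognitive failure". Time to neurocognitive failure has no censoring rule of its own.
- **Analysis.** Section 9(d) says "Other time-to-events data (with or without competing risks) will be analyzed similarly". It has no rule for a missed or impossible test, no recording of the reason, and no sensitivity analysis.
- **Selection bias.** Appendix B wants a battery that most patients can complete, "even patients with significant neurocognitive problems, in order to reduce the likelihood of selection bias". This is a criterion for choosing the tests, not a rule for analysing them. Appendix B refers to the statistical chapter for evaluation of these endpoints, and that chapter adds nothing on the point.
- **When testing stops.** Section 9(a): "Assessments will be conducted every 8 weeks for the first year or until intracranial failure, whichever occurs first"; Section 7(b) agrees. Appendix B: "every 8 weeks until death or until one year after therapy, whichever comes first". Footnote 4 of Appendix C uses one year or a second cerebral progression.

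**The concern.** Kaplan-Meier and cumulative incidence estimates assume that a censored patient has the same outlook as those still followed. A patient who can no longer attempt the battery because of confusion or another neurological problem does not. Being unable to be tested is among the worst cognitive outcomes, yet the plan records it as no failure up to the previous assessment.

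The stake is the rationale in Section 3(e), where cranial TTFields are proposed as an alternative to PCI because they may spare cognition. The trial has one arm, so these estimates will be read on their own, and Section 9(b) justifies the sample size as information for planning the next phase. An error that makes cognition look better than it is would carry into that planning.

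**Working it through.** **The plan's own figures.** The only computed design figures are the intervals in Section 9(b). Two-sided 95% Wilson limits for n = 25 give 10/25: 23.4–59.3%; 15/25: 40.7–76.6%; 18/25: 52.4–85.7%; 20/25: 60.9–91.1%. All match the table after rounding. They concern the primary endpoint. No figure is given for the neurocognitive endpoints, so every rate below is an assumption.

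**Step 1: one visit, rate of decline.** Assume 5 measured declines among 25 living patients, with *u* untestable because of impairment. The plan gives 5/(25 − u); counting the untestable as declined gives (5 + u)/25.

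| u | As planned | Untestable counted |
|---|---|---|
| 2 | 5/23 = 21.7% | 7/25 = 28.0% |
| 3 | 5/22 = 22.7% | 8/25 = 32.0% |
| 5 | 5/20 = 25.0% | 10/25 = 40.0% |

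The 95% Wilson interval for 5/22 is 10–43%, so sampling error is large beside the shift.

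**Step 2: failure-free survival, closed form.** Assume that at each 8-weekly visit pf = 8% of those at risk fail by score and a further pu = 2%, 3% or 5% become untestable. Leaving death aside, the proportion free of failure after six visits is:

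- untestable counted as failure: A = (1 − pf − pu)^6 = 53.1%, 49.7%, 43.4%;
- untestable censored: B = (1 − pf/(1 − pu))^6 = 60.0%, 59.7%, 59.0%;
- untestable kept failure-free until death: C = 1 − [pf/(pf + pu)] × (1 − A) = 62.5%, 63.4%, 65.2%.

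Death is an event in this endpoint, so each figure is multiplied by survival S at the sixth visit, 6 × 56/30.4375 = 11.04 months. With exponential survival, equal for testable and untestable patients, S = 0.5^(11.04/median). The medians come from the two PCI trials in Section 3(a): 6.0 months (within the 5.4 to 6.7 of the EORTC trial), and 10.1 and 15.1 months (the Japanese trial).

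| Median (months) | S | S × (B − A), points, pu = 2 / 3 / 5% | S × (C − A), points, pu = 2 / 3 / 5% |
|---|---|---|---|
| 6.0 | 0.279 | 1.9 / 2.8 / 4.4 | 2.6 / 3.8 / 6.1 |
| 10.1 | 0.469 | 3.2 / 4.7 / 7.3 | 4.4 / 6.4 / 10.2 |
| 15.1 | 0.602 | 4.1 / 6.0 / 9.4 | 5.6 / 8.3 / 13.1 |

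The overstatement is about 2 to 9 points if untestable patients are censored and about 3 to 13 if they are followed to death.

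**Step 3: simulation under different assumptions.** 20,000 patients per scenario, a latent 12-month decline risk of 40%, 25% or 50% of decliners becoming untestable, and the same three medians. Survivors are censored at the last visit before they became untestable; deaths within 12 months count as events. Results at the sixth visit (untestable counted as failure, then as written):

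| Untestable | Median (months) | Time to neurocognitive failure, cumulative incidence | Failure or death |
|---|---|---|---|
| 25% | 6.0 | 20.0 vs 15.2% | 83.5 vs 82.3% |
| 25% | 10.1 | 25.6 vs 19.7% | 72.9 vs 70.4% |
| 25% | 15.1 | 29.0 vs 22.8% | 64.8 vs 62.1% |
| 50% | 6.0 | 20.3 vs 10.3% | 84.2 vs 81.5% |
| 50% | 10.1 | 24.9 vs 13.2% | 72.7 vs 68.5% |
| 50% | 15.1 | 28.7 vs 15.4% | 63.6 vs 57.1% |

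Decline is understated by about 5 to 13 points for time to neurocognitive failure and about 1 to 7 points for failure-free survival. With no untestable patients the two rules agree exactly. The effect is larger on time to neurocognitive failure because a later death there is a competing event and the decline is never counted.

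**The case against.** The strongest reply is that the text says assessment, not completed test. A patient who attempts the battery and recalls or produces no words could be scored at the floor and so recorded as declining, and Section 9(a) itself expects language impairment to show in COWAT results. That stands. A reader might infer that no badly impaired patient can ever fail; the documents do not support so strong a reading. The gap concerns patients who cannot attempt the battery, and for them the ambiguity cures nothing.

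Second, death is an event in failure-free survival. This also stands: for patients who die in follow-up the failure is delayed, and only for survivors is it lost. A reader who used A and B in Step 2 without deaths would infer a bias of 7, 10 or 16 points. Those figures do not describe this endpoint.

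Third, the direction is conditional. Tests missed through systemic illness or refusal need not bias the result this way, and nothing in the documents says how often impairment would be the cause.

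Fourth, the battery was chosen to be brief and widely completable, and neurological examination, KPS and adverse events are recorded every 8 weeks. Severe confusion would thus be documented, but it would not enter these endpoints.

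Finally, these are secondary endpoints with no decision rule, and the plan makes no formal comparison with PCI. Under the censoring version of Step 2 only about 4 to 9 of 25 patients would be counted failure-free at visit six (25 × 16.5% to 25 × 36.1%). Random error may well exceed the bias. That limits the weight of the point, but a larger sample would not remove the bias.

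**Conclusion.** The concern holds in a limited form. The plan leaves patients whose impairment prevents an attempt at testing outside the definition of neurocognitive failure, and the resulting censoring is informative. Decline is understated in all three neurocognitive endpoints, provided the tests are missed because of impairment.

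The size cannot be fixed from the documents. On the assumed rates, failure-free survival at six visits is overstated by about 2 to 9 points (untestable censored) or 3 to 13 (followed to death), or by about 1 to 7 under the simulation's assumptions. Time to neurocognitive failure is understated by about 5 to 13 points, if death is handled as a competing event by analogy with intracranial failure. The survival medians are borrowed from the trials in Section 3(a), and death is assumed no faster in untestable patients; faster death would shrink the followed-to-death figures.

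The primary feasibility endpoint is unaffected. A reader might infer that the cognitive results would be uninterpretable; the documents do not support that. This is a worthwhile, cheap improvement, not a flaw in the trial's main purpose.

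**What to change.** In Section 9(a) and Appendix B:

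- Count a scheduled battery not done because of cognitive or neurological impairment as a neurocognitive failure on the scheduled visit date, and as a decline in that visit's rate.
- Leave batteries missed for any other reason as missing.
- Report the score-only version as a sensitivity analysis.

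Add one CRF field for the reason a test was missed, completed at the visit, because the reason may not be recoverable later.

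Reconcile the stopping rules for testing in Sections 7(b) and 9(a), Appendix B and Appendix C, since the rule above needs an agreed list of scheduled visits. The threshold and number of tests that define a scored failure should be written down at the same time.

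The cost is a few sentences and one CRF field. The downside is that some misses caused by systemic illness may be labelled neurological; the gap between the main and score-only results would show how much that could matter.
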